3.3 Inclusion of Women, Minorities and Other Underrepresented Populations

Women are not relevant for this study in prostate cancer. We will make every effort to include minorities and other underrepresented populations in this trial.

4. REGISTRATION PROCEDURES

4.1 General Guidelines for DF/HCC and DF/PCC Institutions

Institutions will register eligible participants with the DF/HCC Quality Assurance Office for Clinical Trials (QACT) central registration system. Registration must occur prior to the initiation of therapy. Any participant not registered to the protocol before treatment begins will be considered ineligible and registration will be denied.

A member of the study team will confirm eligibility criteria and complete the protocol-specific eligibility checklist.

Following registration, participants may begin protocol treatment. Issues that would cause treatment delays should be discussed with the Principal Investigator. If a participant does not receive protocol therapy following registration, the participant's protocol status must be changed. Notify the QACT Registrar of participant status changes as soon as possible.

4.2 Registration Process for DF/HCC and DF/PCC Institutions

The QACT registration staff is accessible on Monday through Friday, from 8:00 AM to 5:00 PM Eastern Standard Time. In emergency situations when a participant must begin treatment during off-hours or holidays, call the QACT registration line at [contact] and follow the instructions for registering participants after hours.

The registration procedures are as follows:

- 1. Obtain written informed consent from the participant prior to the performance of any study related procedures or assessments.
- 2. Complete the protocol-specific eligibility checklist using the eligibility assessment documented in the participant's medical/research record. To be eligible for registration to the study, the participant must meet each inclusion and exclusion criteria listed on the eligibility checklist.

Reminder: Confirm eligibility for ancillary studies at the same time as eligibility for the treatment study. Registration to both treatment and ancillary studies will not be completed if eligibility requirements are not met for all studies.

3. Fax the eligibility checklist(s) and all pages of the consent form(s) to the QACT at [contact].

Exception: DF/PCC Affiliate sites must fax the entire signed consent form including HIPAA Privacy Authorization and the eligibility checklist to the Network Affiliate Office. The Network Affiliate Office will register the participant with the QACT.

4. The QACT Registrar will (a) validate eligibility, (b) register the participant on the study, and (c) randomize the participant when applicable.

The QACT Registrar will send an email confirmation of the registration and/or randomization to the person initiating the registration immediately following the registration and/or randomization.

5. TREATMENT PLAN

Treatment will be administered on an outpatient basis. Expected toxicities and potential risks as well as dose modifications are described in Section 6 (Expected Toxicities and Dosing Delays/Dose Modification).

The treatment plan is outlined in the table below. Tivozanib will be taken orally once daily for 3 out of 4 weeks on a continuous basis. Enzalutamide will be taken orally once daily without any scheduled interruptions, on a continuous basis.

| Treatment Description | | | | | | |
|-----------------------|-------------|--------|---------------|------------|-----------------|--|
| Agent | Precautions | Dose | Route | Schedule | Cycle Length | |
| Tivozanib | None | 1.5 mg | PO once daily | Weeks 1-3 | | |
| Enzalutamide | None | 160 mg | PO once daily | Continuous | 28 days | |

Because this combination has not been previously tested, a safety run-in will be conducted at the outset of the trial. After the first 3 patients are enrolled, accrual will be held until all three patients complete the first 1 month of treatment. Additionally, after a total of 10 patients are enrolled, these patients will be analyzed for safety and toxicity by the DSMC. If any treatment-related, expected or unexpected grade 3 or higher adverse events occur during the first month of treatment in the first 3 patients, or if the rate is >30% among the first 10 patients during the first month of treatment, further accrual will be halted for reconsideration of the appropriateness of the dosing schedules.

5.1 Pre-treatment Criteria

All subjects must have the following within 21 days prior to start of protocol therapy:

- History and physical examination
- ECOG performance status
- Vital signs (including blood pressure, body temperature, heart rate and respiratory rate)
- Availability and review of prior medical records
- Concomitant medications
- Adverse event assessments
- Serum PSA
- Serum testosterone
- Complete blood count
- Serum chemistries
- Thyroid function test (TSH only)
- Coagulation studies
- Urinalysis (urine protein only)
- Electrocardiogram
- Chest x-ray

- Bone scan (repeat scans every 3 cycles up to Cycle 46 then repeat every 6 cycles)
- Abdomen/pelvic CT scan (repeat scans every 3 cycles up to Cycle 46 then repeat every 6 cycles)

Based on these studies, eligibility must be confirmed according to the guidelines in Section 3 above.

5.1.1 Day 1 of Cycle 1

The following data should be collected on Cycle 1 Day 1 (+/- 3 days):

- History and physical exam
- Concomitant medications
- Vital signs (including blood pressure, body temperature, heart rate and respiratory rate)
- ECOG performance status
- Complete blood count
- Serum chemistries
- Urinalysis (urine protein only)
- Adverse event assessments

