3. PARTICIPANT SELECTION

3.1 Eligibility Criteria

Participants must meet the following criteria on screening examination to be eligible to participate in the study:

- **3.1.1** Participants must have adenocarcinoma of the prostate that is metastatic or unresectable and for which standard curative options do not exist
- **3.1.2** Participants must have radiographic evidence of metastatic prostate cancer
- **3.1.3** Participants must have progressive disease despite ongoing androgen deprivation therapy (ADT) and castrate levels of testosterone, defined as castration resistant prostate cancer (CRPC)
- **3.1.4** Other than ongoing ADT, prior treatment with other hormonal agents such as antiandrogens or ketoconazole must have been stopped at least two weeks prior to enrollment

- **3.1.5** Participants may have received prior docetaxel-based chemotherapy for prostate cancer. Such chemotherapy must have been stopped at least three weeks prior to the first dosing in this study.
- 3.1.6 Male patients age ≥ 18 . Because no dosing or adverse event data are currently available on the use of enzalutamide or tivozanib in participants <18 years of age, children are excluded from this study.
- **3.1.7** Life expectancy of greater than 12 weeks
- **3.1.8** ECOG performance status ≤ 2
- **3.1.9** Participants must have normal organ and marrow function as defined below:
 - Absolute neutrophil count ≥ 1,500/mcL
 - Platelets $\geq 50,000/\text{mcL}$
 - total bilirubin $\leq 1.5 \times \text{ULN}$ (or $\leq 2.5 \times \text{ULN}$ for subjects with

asymptomatic Gilbert's syndrome)

- AST (SGOT)/ALT (SGPT) ≤ 2.5 X institutional upper limit of normal
- Creatinine $\leq 2x$ ULN
- Proteinuria < 3+ by urinalysis or urine dipstick
- **3.1.10** The effects of tivozanib and enzalutamide on the developing human fetus are unknown. For this reason, participating men must agree to use adequate contraception (hormonal or barrier method of birth control; abstinence) prior to study entry and for the duration of study participation.
- **3.1.11** Ability to understand and the willingness to sign a written informed consent document.

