3.2 Exclusion Criteria

Participants who exhibit any of the following conditions at screening will not be eligible for admission into the study.

- **3.2.1** Prior treatment with enzalutamide, TOK-001, or ARN-509. Prior therapy with abiraterone or orteronel is permitted, but must have been stopped a minimum of two weeks prior to study entry. Prior and/or concurrent treatment with bone-targeted therapy such as bisphosphonates or denosumab is permitted.
- **3.2.2** Participants who have received more than two prior chemotherapy regimens for metastatic CRPC
- **3.2.3** Participants may not be receiving any other investigational anticancer agents

- **3.2.4** Participants with known brain metastases
- **3.2.5** History of allergic reactions attributed to compounds of similar chemical or biologic composition to tivozanib or enzalutamide
- **3.2.6** Radiotherapy or minor surgical procedure within 2 weeks, or major surgical procedure within 4 weeks prior to administration of first dose of study drug; inadequate recovery from prior surgical procedure
- **3.2.7** Any history of seizure or condition that may predispose to seizure
- **3.2.8** Significant cardiovascular disease, including
 - Uncontrolled hypertension: systolic blood pressure > 140 mmHg and/or diastolic blood pressure > 90 mmHg documented on 2 consecutive measurements taken at least 24 hours apart;
 - Myocardial infarction, severe angina, or unstable angina within 6 months prior to administration of first dose of study drug;
 - History of Class III or IV congestive heart failure, as defined by the New York Heart Association;
 - History of serious ventricular arrhythmia (ie, ventricular tachycardia or ventricular fibrillation):
 - Cardiac arrhythmias requiring anti-arrhythmic medications (except for atrial fibrillation that is well-controlled with anti-arrhythmic medication; and/or
 - Coronary or peripheral artery bypass graft within 6 months of screening
- **3.2.9** Non-healing wound, bone fracture or skin ulcer
- **3.2.10** Active peptic ulcer disease, inflammatory bowel disease, ulcerative colitis, or other gastrointestinal condition with increased risk of perforation; history of abdominal fistula, gastrointestinal perforation, or intra-abdominal abscess within 4 weeks prior to administration of first dose of study drug
- **3.2.11** Serious/active infection or infection requiring parenteral antibiotics

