8. STUDY CALENDAR

Baseline evaluations are to be conducted within 3 weeks prior to start of protocol therapy. Subsequent evaluations should be carried out on Day 1 of subsequent cycles (+/- 3 days) every 12 weeks from Cycle 46 on. Radiographic evaluations including bone and abdominal/pelvic CT scans should be conducted at baseline and every 24 weeks from Cycle 46 on.

| | Pre- Study | Cycle 1 Day 1 ^x | Cycle 2 to Cycle 45, Day 1 ^x | Day 1 Cycles ≥ 46, Every 12 Weeks ^x | Off Study ^b |
|---|---------------|-------------------------------|---|--|------------------------|
| Treatment Schedule: | | | | | |
| Tivozanib | | X (days 1-21) | X (days 1-21) | X (days 1-21) | |
| Enzalutamide | | X (Days 1-28) | X (days 1-28) | X (days 1-28) | |
| Informed consent | X | | | | |
| Demographics | X | | | | |
| Medical/Interval history | X | X | X | X | X |
| Concurrent meds | X | X | X | X | X |
| Physical exam | X | X | X | X | X |
| Vital signs/ BP | X | X | X | X | X |
| Performance status | X | X | X | X | X |
| Serum PSA | X | | X | X | X |
| PT, PT/INR, and PTT | X | | | | |
| CBC w/diff, plts | X | X | X | X | X |
| Serum chemistry ^a | X | X | X | X | X |
| Serum testosterone | X | | | | |
| Thyroid Function (TSH only) | X | | X (odd cycles) | X | |
| Urinalysis (urine protein only) | X | X | X | X | X |
| Chest xray | X | | as clinicall | y indicated | |
| Bone scan and abdominal/pelvis CT scans | X | Rep | Repeat scans every 24 weeks | | X ^c |
| EKG | X | | | | |
| Adverse Event Evaluation | X | Х | | | -X |
| Survival follow-up | | | | | X ^d |

x: ± 3 days for treatment or assessment requirement

MEASUREMENT OF EFFECT

a: Sodium, potassium, chloride, BUN, creatinine, glucose, albumin, total protein, total bilirubin, alkaline phosphatase, SGOT [AST], SGPT [ALT]

b: Off-study evaluation should occur within 30 days after the last dose of study treatment c: Post-treatment scans will be performed if an assessment has not been performed within the prior 6 weeks

d: Follow for survival information every 3 months until death, up to 2 years after discontinuing therapy, or patient lost to follow-up

The primary endpoint of the study is progression free survival (PFS). Secondary clinical endpoints will include safety, overall survival, time to PSA progression, PSA response rate and objective response rate.

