9.2 Other Response Parameters

9.2.1 Time to PSA Progression

PSA progression will be defined according to the consensus guidelines of PCWG2¹⁵. For patients with PSA declines at Week 13, the PSA progression date is defined as the date that a $\geq 25\%$ increase and an absolute increase of ≥ 2 ng/mL above the nadir is documented, which is confirmed by a second consecutive value 3 or more weeks later. For patients with no PSA decline at Week 13, the PSA progression date is defined as the date that a $\geq 25\%$ increase and an absolute increase of ≥ 2 ng/mL above the baseline is documented, which is confirmed by a second consecutive value 3 or more weeks later.

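### The only scheduled pre-treatment PSA may be up to 21 days old at first dose, so PSA change before dosing can enter two secondary endpoints

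*Combined protocol and SAP*

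**What the plan says.** Section 5.1 introduces the screening list, which includes serum PSA, with "All subjects must have the following within 21 days prior to start of protocol therapy". The study calendar (Section 8) sets the same limit: "Baseline evaluations are to be conducted within 3 weeks prior to start of protocol therapy".

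Section 5.1.1 opens with "The following data should be collected on Cycle 1 Day 1 (+/- 3 days") and lists eight items. Complete blood count and serum chemistries are among them; PSA is not. The calendar agrees. Its PSA row reads "Serum PSA | X | | X | X | X", with the Cycle 1 Day 1 cell blank. The next PSA is in the Cycle 2 to 45 column or, by Section 5.1.2, at the every-third-cycle visits. A note in 5.1.2 waives repeat hematology, chemistry, urinalysis and some other assessments if they were done in the 7 days before Cycle 1 Day 1. PSA is not covered by that note.

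On washout, 3.1.4 says that "prior treatment with other hormonal agents such as antiandrogens or ketoconazole must have been stopped at least two weeks prior to enrollment", and 3.2.1 says "Prior therapy with abiraterone or orteronel is permitted, but must have been stopped a minimum of two weeks prior to study entry". Section 5.3.1 repeats the two-week rule. None of these refers to the PSA draw. Section 4.1 requires registration before therapy but sets no minimum or maximum gap.

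Section 9.2.1 measures PSA progression from the nadir for men whose PSA has declined at Week 13. The other men get a different reference: "For patients with no PSA decline at Week 13, the PSA progression date is defined as the date" of a rise of at least 25% and at least 2 ng/mL above baseline, confirmed 3 or more weeks later. Section 10.2.3 defines PSA response by citing PCWG2 and writes out no threshold or reference value.

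**The concern.** PSA response and time to PSA progression are stated secondary objectives (Section 1.3). Both need a reference value that reflects PSA when study treatment starts. The screening PSA is the only pre-treatment value scheduled, so it is the only planned reference, and it can be three weeks old. All eligible men have progressive disease (3.1.3), so a rise over those weeks is plausible. Stopping a prior hormonal agent could also move PSA, in a direction and by an amount the documents do not give.

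The trial has a single arm, so no concurrent control shares and cancels the drift. Its size depends on how early a man was screened and how fast his PSA was moving. Neither is an effect of treatment. At stake are the accuracy of the PSA response rate, the choice between nadir and baseline as the progression reference, and the progression date in men with no Week 13 decline.

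**Working it through.** **The plan's own figure.** No sample size, power or precision is stated for a PSA endpoint, so there is no PSA figure to reproduce. The main design figure is 80% power for PFS (Section 14.1: 20 events, hazard ratio 0.625, one-sided 10%). The exact one-sample exponential calculation, P(χ²₄₀ > 0.625 × χ²₄₀,₀.₉₀), gives 79.9%. The stated figure reproduces and does not depend on PSA.

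**Inputs.** From the documents: a maximum gap of 21 days from PSA draw to first dose (5.1, Section 8); washout of at least 14 days before enrollment or study entry (3.1.4, 3.2.1, 5.3.1); a progression rule of at least 25% and at least 2 ng/mL, confirmed (9.2.1). Assumed: exponential PSA growth, doubling times (DT) of 2, 3 and 6 months at 30.4 days per month, and response taken as a 50% fall.

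**Step 1, growth before dosing.** The factor is f = 2^(gap/DT). With a 21-day gap:

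| Assumed DT | f | Rise before dosing | True fall needed to record 50%: 1 − 0.5/f | True fall needed to record any decline: 1 − 1/f | Rise from dosing level that reaches +25% over baseline: 1.25/f − 1 |
|---|---|---|---|---|---|
| 2 months | 1.270 | 27.0% | 60.6% | 21.3% | −1.6% (already passed) |
| 3 months | 1.173 | 17.3% | 57.4% | 14.8% | 6.6% |
| 6 months | 1.083 | 8.3% | 53.8% | 7.7% | 15.4% |

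True falls are measured from the day-of-dosing level. The any-decline column bears on the Week 13 split.

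**Step 2, shorter gaps.** At 7 days the rises are 8.3%, 5.5% and 2.7%, and the true falls needed to record 50% are 53.8%, 52.6% and 51.3%. At 3 days the rises are 3.5%, 2.3% and 1.1%. At 0 days there is no drift.

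**Step 3, when the 25% margin is used up before dosing.** Solving 2^(21/DT) = 1.25 gives DT = 21 × ln 2 / ln 1.25 = 65 days. The absolute criterion must also be met: a 27% rise amounts to 2 ng/mL only if baseline PSA is at least 2/0.27 = 7.4 ng/mL. Confirmation and the absence of a Week 13 decline are still required.

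**Step 4, the other direction.** If PSA fell by 10%, 20% or 30% before dosing (assumption), the true fall that would be recorded as 50% is 1 − 0.5/0.9 = 44%, 1 − 0.5/0.8 = 38% or 1 − 0.5/0.7 = 29%.

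**Step 5, overlap with prior hormonal therapy.** Let k be the days from registration to first dose, and count the washout back from registration. The days of the PSA window that can fall on prior therapy are max(0, 21 − 14 − k): 7 for k = 0, 4 for k = 3, 1 for k = 6, and 0 for k of 7 or more.

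**The case against.** A baseline taken in a screening window is a consistent design choice, the same in text and calendar. PFS rests on radiographic or clinical progression or death (9.1.4, 14.1), so the primary analysis is untouched. PSA response is estimated with an exact interval (14.3), and no hypothesis or decision rule depends on it. Twenty-one days is the limit, not the typical gap. A pre-dose rise understates response and brings baseline-referenced progression forward, so it does not create a false signal of activity.

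Most of this stands, and it limits the point to secondary endpoints. It does not remove it: these endpoints are meant to estimate a treatment effect, the error can also run the other way (Step 4), and a gap that varies between men adds noise unrelated to treatment.

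Two stronger readings are tempting. A reader might infer that the plan lets baseline PSA be drawn while a man is still on abiraterone or another hormonal agent. That needs registration less than 7 days before dosing and a draw early in the window. It also needs the washout not to be complete at screening, whereas the opening sentences of 3.1 and 3.2 apply the criteria at screening. A reader might also infer that a man with a short doubling time has progressed by PSA before his first dose. Section 9.2.1 does not allow that: the 2 ng/mL rise, the confirmation and the absence of a Week 13 decline all have to hold.

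The reach of a remedy is a fair doubt too. The protocol version is dated 11.19.2020 and the calendar schedules visits from Cycle 46, after 45 × 28 = 1,260 days (about 3.5 years) of treatment, against a planned 21-month accrual. If accrual has ended, which is only an inference, a new Cycle 1 Day 1 draw helps no one.

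**Conclusion.** The point holds for secondary endpoints. As written, the reference PSA can be up to 21 days old at first dose, nothing fresher is scheduled, and baseline is not otherwise defined. Pre-dose change can enter PSA response, the Week 13 classification and, for men with no decline, the progression date. Men with a Week 13 decline are measured from nadir and are unaffected unless that classification changes.

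At the maximum gap the drift is about 27%, 17% or 8%, and a recorded 50% fall needs a true fall of about 61%, 57% or 54%. These figures rest on assumed doubling times of 2, 3 and 6 months, on exponential growth, and on a 50% threshold that the protocol does not state. The response part also assumes that the screening PSA is the reference, which the protocol implies but does not say. At a doubling time of about 65 days or less the 25% relative margin can be used up before dosing, but that alone does not make a progression event.

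The documents do not establish that baseline PSA will be drawn on prior hormonal therapy. They fail to tie the draw to the washout; any overlap is conditional, at most 7 days, and of unknown direction.

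**What to change.** Add serum PSA to Cycle 1 Day 1 in Section 5.1.1 and in the calendar, stating that it is drawn before the first dose despite the ±3-day window. Let a screening PSA stand instead only if drawn within 7 days before Day 1, in line with the note already in 5.1.2. In Sections 9.2.1 and 10.2.3, define baseline PSA as the last value before first dose, drawn after prior hormonal agents were stopped.

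For men already dosed, apply the last-pre-dose-value rule and report the interval from PSA draw to first dose, so that readers can judge how much drift is possible.

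The cost is at most 42 extra PSA assays, alongside laboratory tests already scheduled that day, and a short definition. Eligibility, washout, dosing, PFS and sample size do not change.

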5.1.2 Day 1 of Every 3rd Cycle

The following data should be collected on Day 1 (+/- 3 days) of every 3rd cycle (see Schedule of Events):

- History and physical examination
- ECOG performance status
- Vital signs (including blood pressure, body temperature, heart rate and respiratory rate)
- Complete blood count
- Serum chemistries
- Thyroid function test (TSH only; every odd number Cycle beyond Cycle 1 up to Cycle 46 and then every 3rd Cycle)
- Urinalysis (urine protein only)
- Serum PSA
- Concomitant medications
- Adverse event assessments
- Study drug diary

[Note: If ECOG performance status, physical examination, hematology, serum chemistry, coagulation studies, and urinalysis were measured/performed within 7 days prior to Cycle 1, Day 1, they need not be repeated at that visit.]

If any treatment-related grade ≥ 3 non-hematologic or grade ≥ 4 hematologic adverse events are observed, then treatment should be held until resolution of the event(s) to \leq grade 2. The attribution of the events to either or both of the study drugs will be at the discretion of the treating physician, and only the responsible drug should be held. Doses that are held will not be

made up, and the cycle number and cycle day will continue chronologically regardless of whether treatment is held.

If either study drug is held for \geq 4 weeks, regardless of cause, then the patient should be removed from study treatment.

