6.2 Tivozanib Dose Modification

Clinical judgment will be used to determine appropriate management of the subject experiencing any adverse event (AE). The suggested criteria for dose modification for tivozanib hydrochloride drug-related AEs (excluding hypertension) are summarized in the table below.

Tivozanib Hydrochloride Dose Modification Guidelines for Drug-Related Adverse Events

| Drug-Related Adverse | Action Taken | Subsequent Dosing Modification |
|-----------------------------|--|---|
| Events (excluding | | |
| Hypertension ^a) | | |
| Grade 1 | No dose interruption, or reduction required; adverse event management is at the discretion of the Investigator | None required; Dosing may continue at the same dose |
| Grade 2 | No dose interruption, or reduction required; adverse event management is at the discretion of the Investigator | None required; Dosing may continue at the same dose |
| Grade 3 | Interrupt dosing until toxicity resolves to baseline. | Dosing may resume at same dose or reduced dose at the discretion of the Investigator (see below for dose reduction guidelines). |
| Grade 4 | Interrupt dosing until toxicity resolves to baseline. | Dosing may resume at same dose or reduced dose at the discretion of the investigator (see below for dose reduction guidelines). |

^a Hypertension must be treated as described in Section 6.2.1 prior to any dose modification

If a patient experiences unacceptable toxicity related to tivozanib at 1 mg/day, he should be removed from study. Once the dose of tivozanib is reduced, it should not be re-escalated throughout the study.

Subjects with clinically significant Grade 3/4 AEs that are assessed as possibly, probably or definitely study drug-related by the Investigator should have their dose interrupted to allow for resolution of toxicities to baseline. The exception is HTN, which must first be treated as described in Section 6.2.1 prior to any dose modification. Tivozanib may be held for up to 4 weeks. If any drug-related toxicity results in interruption of > 4 weeks, the subject should be discontinued from the study.

Dose escalation of tivozanib above 1.5 mg/day will not be allowed.

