6.2.1. Management of Hypertension

Hypertension (HTN) that occurs during study treatment must be treated with anti-hypertensive drugs prior to any dose reduction. Recommended management of HTN for subjects receiving study drug is presented in Appendix C.

Persistent HTN is defined as 2 consecutive elevated blood pressure (BP) measurements preferably taken in the clinic and obtained at least 1 hour apart. It is recommended that 24-48 hours should elapse between the decision steps. For a listing of recommended DHP (dihydropyridine) calcium channel blockers, angiotensin converting enzyme (ACE) inhibitors, and angiotensin receptor blockers, see Appendix C, Recommended Antihypertensive Medications. Note: If a subject has controlled HTN on an anti-hypertensive regimen at baseline and then develops a worsening of HTN requiring more intensive therapy then the previous regimen, this would be considered Grade 3 HTN.

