6.4 Enzalutamide Dose Modification

Dose modification of enzalutamide will generally not be permitted. Patients who experience Grade 3 or greater toxicity related to enzalutamide that cannot be ameliorated by the use of adequate medical intervention should have treatment interrupted until the toxicity improves to Grade 2 or lower severity. A treatment break of up to 4 weeks is permitted. If a patient experiences unacceptable toxicity related to enzalutamide at 160 mg/day, he should be removed from study unless specific permission to restart at a reduced dose is granted by the PI.

Dose escalation of enzalutamide above 160 mg/day will not be allowed.

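### Section 5.1.2 gives different rules from Sections 6.2 and 8 on holding tivozanib for hypertension, on resuming it, and on visits in Cycles 2 to 45

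*Combined protocol and SAP*

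**What the plan says.** **Holding.** Section 5.1.2 reads: "If any treatment-related grade ≥ 3 non-hematologic or grade ≥ 4 hematologic adverse events are observed, then treatment should be held until resolution". The treating physician decides which drug is responsible, and only that drug is held. Hypertension is not mentioned. Section 6.2 has its own rule for tivozanib. It addresses "Subjects with clinically significant Grade 3/4 AEs that are assessed as possibly, probably or definitely study drug-related by the Investigator" and says that they "should have their dose interrupted to allow for resolution of toxicities to baseline. The exception is HTN, which must first be treated". The sentence goes on to name Section 6.2.1 as the route for that treatment and puts it ahead of any dose modification. Section 6.2.1 adds a grading rule: "If a subject has controlled HTN on an anti-hypertensive regimen at baseline and then develops a worsening of HTN requiring more intensive therapy" than before, "this would be considered Grade 3 HTN".

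**Resuming.** Section 5.1.2 lifts the hold once the event is at grade 2 or lower. Section 6.2, in both its table and its text, interrupts tivozanib until the toxicity is back to baseline. It then sets a limit: "If any drug-related toxicity results in interruption of > 4 weeks, the subject should be discontinued from the study".

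**Visits.** The heading and first sentence of 5.1.2 put the assessments on Day 1 of every third cycle, refer to the Schedule of Events, and give no cycle range. The TSH line in the same list asks for odd-numbered cycles up to Cycle 46. The table in Section 8 has a Day 1 column for Cycles 2 to 45 and a separate 12-weekly column that begins at Cycle 46. Section 5.2.2 speaks of study visits every 12 weeks when it describes drug return and accountability.

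**The concern.** These are instructions that sites act on, for a combination that the protocol says had not been tested before.

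- **Hypertension.** Two sites can follow the protocol and still treat the same man differently. One stops tivozanib at once for related grade 3 hypertension; the other starts or raises antihypertensives and continues dosing. The grading rule in 6.2.1 makes this easy to reach, because a man with controlled hypertension at entry counts as grade 3 as soon as he needs more intensive therapy.
- **Resuming.** If a grade 3 toxicity settles at grade 2 but stays above baseline, 5.1.2 allows re-dosing. Section 6.2 keeps tivozanib off and discontinues the patient if the interruption passes 4 weeks.
- **Visits.** Scheduled blood pressure, laboratory and urine protein checks differ about threefold. The run-in rule counts first-month events, and only Section 8 has a scheduled visit at the end of that month.

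**Working it through.** **Dosing rules side by side (tivozanib)**

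| | Section 5.1.2 | Sections 6.2 and 6.2.1 |
|---|---|---|
| Related grade 3 or higher hypertension | Hold, no exception | Treat first, then consider dose modification |
| When dosing resumes | Grade 2 or lower | Baseline |

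The exception in 6.2 follows directly on the sentence about interrupting the dose, so it covers holds as well as reductions. Antihypertensives and a hold can be given together, so the hypertension conflict is narrow: is the hold immediate? For resumption, waiting until baseline satisfies both texts. The difference is that 5.1.2, read alone, permits earlier re-dosing. Section 6.4 also uses grade 2 for enzalutamide, so the resumption conflict concerns tivozanib only.

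**Visit count, Cycles 2 to 45**

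- Section 8: 45 − 2 + 1 = 44 visits.
- Section 5.1.2, read as Cycles 3, 6, …, 45: 45/3 = 15 visits.
- Section 5.1.2, read as Cycles 4, 7, …, 43: (43 − 4)/3 + 1 = 14 visits.
- Ratio: 44/15 = 2.9 to 44/14 = 3.1.

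**TSH line against its own heading.** Odd cycles from 3 to 45 number (45 − 3)/2 + 1 = 22. On the 3, 6, 9 reading, 8 of them (3, 9, …, 45) coincide with a visit and 14 do not. On the 4, 7, 10 reading, 7 (7, 13, …, 43) coincide and 15 do not.

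**Timing.** With 28-day cycles, Day 1 of cycle c is study day 28(c − 1) + 1.

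- Cycle 2: Day 29, the end of the run-in month. Section 8 has a visit here; 5.1.2 has none.
- Cycle 3: Day 57 (Week 9). Cycle 4: Day 85 (Week 13). One of these is the first scheduled visit after Cycle 1 Day 1 under 5.1.2.
- Cycle 46: 45 × 28 = 1,260 days, or 180 weeks, or about 41.4 months after Cycle 1 Day 1.

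Section 14.1 assumes exponential PFS with a median of 14 months (control) or 22.4 months (target). The share with a PFS event by 41.4 months is 1 − 2^(−41.4/14) = 0.87 or 1 − 2^(−41.4/22.4) = 0.72. This is PFS, not time on treatment. Since treatment ends at progression or earlier, most patients would spend their whole treatment in the period where the two schedules disagree.

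**The case against.** The strongest reply is that the protocol already shows which text governs. Section 5 says that dose modifications are described in Section 6, the hypertension exception in 6.2 is a specific rule against a general one, and 5.1.2 itself refers to the Schedule of Events. Section 6.2 also opens with clinical judgment and calls its table suggested, and the Appendix C figure on hypertension, which is not visible here, may settle when to hold. This shows which way to conform the text, and that the hypertension conflict is one of timing. It does not cancel the different rules that 5.1.2 states, and no clause gives one section precedence.

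On visits, 5.1.2 is not alone: 5.2.2 does refer to study visits every 12 weeks. The every-third-cycle heading may have been meant for Cycle 46 onward, but the text does not say so. The sponsor's intention is therefore not certain.

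Four stronger readings are tempting and are not supported.

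- *A count of affected patients.* Section 2.1.1.3 gives any-grade hypertension of 22.2% (related, combination studies) and 42.4% (treatment-emergent, pooled renal cell studies); Section 6.1 gives 44.9%. The grade 3 share is not given, and 5.1.2 applies only to related events. Any count would rest on an assumed share.
- *The run-in would miss its events.* Section 6.2 collects adverse events from the first dose, and Section 12.1 requires an adverse event form each cycle. What remains is a risk to events found only by measurement, such as asymptomatic blood pressure or laboratory changes.
- *The Week 13 PSA in 9.2.1 would be missed.* That follows only from a Cycle 3, 6, 9 reading, which draws PSA in Weeks 9 and 21. Twelve weeks from Cycle 1 Day 1 is Cycle 4 Day 1, and 7.1.2 dispenses 63 tivozanib days, or three cycles. Both favour Cycles 4, 7, 10, which include Week 13.
- *Section 6 should replace 5.1.2 throughout.* The texts differ elsewhere too. Grade 3 hematologic events are interrupted under 6.2 but not held under 5.1.2. Section 6.4 interrupts enzalutamide only for "Grade 3 or greater toxicity related to enzalutamide that cannot be ameliorated by the use of adequate medical intervention". Section 5.1.2 removes a patient at 4 weeks or more, whereas 6.4 says "A treatment break of up to 4 weeks is permitted"; the two part only at exactly 28 days. Nothing in the documents argues for moving those thresholds.

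**Conclusion.** The three conflicts are in the current text and should be corrected. Section 5.1.2 differs from 6.2 on whether related grade 3 or higher hypertension means an immediate tivozanib hold, and on whether tivozanib resumes at grade 2 or at baseline. It differs from Section 8 on visit frequency before Cycle 46: 14 or 15 visits against 44. The visit counts follow from the text alone; the 72% to 87% figure rests on the exponential PFS assumption in Section 14.1. The dosing conflicts have no patient count attached, because the documents do not give one. The point is about safety monitoring and consistency between sites; the primary analysis and sample size are unaffected.

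**What to change.** 1. In 5.1.2, add: *For tivozanib, resume only when the event has resolved to baseline (Section 6.2). Grade 3 hypertension is first treated under Section 6.2.1 before tivozanib is held; grade 4 hypertension is held at once.* Leave the other hold triggers in 5.1.2 unchanged, including the hematologic threshold and the enzalutamide rule. The grade 4 clause keeps the only automatic hold for grade 4 hypertension that is visible in the documents. The exception in 6.2 covers grade 4 as well, so the same clause should be repeated there. The sponsor should check it against the Appendix C figure.
2. Retitle 5.1.2, and change its first sentence, to *Day 1 of Cycles 2-45, then every 12 weeks from Cycle 46*, matching Section 8. In 5.2.2, state that before Cycle 46 the 12-week interval is for drug return and accountability. This keeps blood pressure, laboratory and adverse event checks at Cycle 2 Day 1, the end of the run-in month.

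The cost is wording only if Section 8 is the intended schedule. If sites now follow 12-weekly visits before Cycle 46, their visits rise about threefold, to the number that Section 8 already requires.
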